8.3.3 Lifestyle Restrictions

1. Subjects are to refrain from strenuous exercise and contact sports from 96 hours prior to screening, admission, and for the duration of the study as this could result in abnormal clinical laboratory values.
2. Subjects are not permitted to consume alcohol-containing beverages from 72 hours prior to (first) admission to the CRU until completion of all follow-up visits at study discharge (Part A and B) and from 72 hours prior to each visit to the CRU and during the stays in the CRU (Part C).
3. Subjects are not permitted to consume caffeine-containing food or beverages from 72 hours prior to admission to the CRU until 24 hours after the last dose (Part A and B), and from 72 hours prior to admission to the CRU and during the stays in the CRU (Part C).
4. Subjects are not permitted to consume any nutrients known to modulate CYP enzymes activity (eg, grapefruit or grapefruit juice, pomelo juice, star fruit, or Seville [blood] orange products) within 14 days prior to first administration of study drug until after discharge in the last treatment period.
5. Subjects are not allowed to smoke or use smoking cessation or nicotine containing products (including, but not limited to, e-cigarettes, pipes, cigars, chewing tobacco, nicotine patches, nicotine lozenges, or nicotine gum, varenicline, bupropion) within 6 months of the first dose of study until after discharge in the last treatment period.
6. Subjects are required to fast overnight with an additional 4 hours of fasting post-dose on the following study days: Day 1 (Part A), Day 1 and Day 14 (Part B and Part C [intensive PK sampling sub-cohort only]).
7. Subjects should refrain from consumption of any foods containing poppy seeds within 48 hours (2 days) prior to screening and admission to the clinical research center to avoid false positive drug screen results.

8.3.4 Screen Failures and Rescreening

Screen failures are defined as subjects who consent to participate in the clinical study but are not subsequently randomized in the study for any reason. A minimal set of screen failure information is required to ensure transparent reporting of screen failure subjects, to meet the Consolidated Standards of Reporting Trials (CONSORT) publishing requirements, and to respond to queries from regulatory authorities. Minimal information includes date of consent, demography, screen failure details, eligibility criteria, and any serious adverse events (SAEs).

The study permits the rescreening (after the end of the initial 3-week screening period) of a subject who discontinues the study as a pretreatment failure (ie, the subject failed screening and has not been treated). The subject must be re-consented and will be assigned a new identification number, and a full screening visit must be performed again.

Screening assessments and/or laboratory parameters (Section 1) may be repeated at the Investigator's discretion, in an effort to find all possible well-qualified subjects. Consultation

with the PRA Medical Monitor may be needed to identify whether repeat testing of any particular parameter is clinically relevant.

8.3.5 Withdrawal and Replacement of Subjects

8.3.5.1 Discontinuation of Treatment

Subjects MUST discontinue IP or study procedures (in case of single dose treatments) for any of the following reasons:

- Subject's request to stop study treatment. Subjects who request to discontinue study treatment will remain in the study and must continue to be followed for protocol specified follow-up procedures. The only exception to this is when a subject specifically withdraws consent for any further contact with him/her or persons previously authorized by subject to provide this information.
- Any clinical AE, laboratory abnormality or intercurrent illness which, in the opinion of the Investigator, indicates that continued participation in the study is not in the best interest of the subject.
- Termination of the study or program by BMS.
- Loss of ability to freely provide consent through imprisonment or involuntarily incarceration for treatment of either a psychiatric or physical (eg, infectious disease) illness.
- Abnormal liver tests suggestive of drug-induced liver injury (DILI) as defined in Section 8.5.2.1.7.
- Inability to comply with protocol.
- Stopping rules as defined in Section 8.3.5.5 are met.
- Discretion of the Investigator.

If study treatment is discontinued prior to the subject's completion of the study, the reason for the discontinuation must be documented in the subject's medical records and entered on the appropriate electronic case report form (eCRF) page. As indicated, appropriate follow-up and/or alternate medical care must be arranged for the subject.

Refer to the Schedule of Activities (Section 1) for data to be collected at the time of treatment discontinuation and follow-up and for any further evaluations that can be completed.

All subjects who discontinue study treatment should comply with protocol specified follow-up procedures as outlined in Section 1. The only exception to this requirement is when a subject withdraws consent for all study procedures including post-treatment study follow-up or loses the ability to consent freely (ie, is imprisoned or involuntarily incarcerated for the treatment of either a psychiatric or physical illness). Replacement of subjects is described in Section 8.3.5.4.

To the greatest extent possible, subjects who discontinue study treatment will remain in the study for continued follow-up.

In the case of pregnancy (Section 8.5.2.1.5), the Investigator must immediately notify the BMS Study Director and PRA Medical Monitor or designee of this event. In the event a normal healthy female subject becomes pregnant during a clinical trial, the study treatment must be discontinued immediately. In most cases, the study treatment will be permanently discontinued in an appropriate manner (eg, dose tapering if necessary for subject safety). Please call the BMS Study Director and PRA Medical Monitor within 24 hours of awareness of the pregnancy.

8.3.5.2 Discontinuation from the Study

Subjects who request to discontinue study treatment will remain in the study and must continue to be followed for protocol specified follow-up procedures. The only exception to this is when a subject specifically withdraws consent for any further contact with him/her or persons previously authorized by subject to provide this information. Expectations are as follows:

- Subjects should notify the Investigator of the decision to withdraw consent from future follow-up in writing, whenever possible.
- The withdrawal of consent should be explained in detail in the medical records by the Investigator, as to whether the withdrawal is from further treatment with study treatment only or also from study procedures and/or post-treatment study follow-up, and entered on the appropriate eCRF page.
- In the event that vital status (whether the subject is alive or dead) is being measured, publicly available information should be used to determine vital status only as appropriately directed in accordance with local law.
- If the subject withdraws consent for disclosure of future information, the Sponsor may retain and continue to use any data collected before such a withdrawal of consent.

The following procedures must be performed upon subject withdrawal:

- Assessments for the end of treatment visit must be performed, provided that the subject has not withdrawn consent for these activities.
- All required eCRF pages must be completed, including the date of and explanation for the withdrawal.

8.3.5.3 Lost to Follow-up

All reasonable efforts must be made to locate subjects to determine and report their ongoing status. This includes follow-up with persons authorized by the subject as noted above. Lost to follow-up is defined by the inability to reach the subject after a minimum of 3 documented phone calls, faxes, or emails as well as lack of response by subject to 1 registered mail letter. All attempts should be documented in the subject's medical records. If it is determined that the subject has died, the site will use permissible local methods to obtain the date and cause of death.

The site staff will consult publicly available sources, such as public health registries and databases, in order to obtain updated contact information. If after all attempts, the subject remains lost to follow-up, then the last known alive date as determined by the Investigator should be reported and documented in the subject's medical records.

8.3.5.4 Replacement of Subjects

Rescreening is discussed in Section 8.3.4.

Subjects will not be replaced if they are discontinued from the study secondary to an AE unless the AE can be determined to be unrelated to treatment. Subjects who are discontinued from the study for reasons not related to an adverse or other safety observation may be replaced. The replacement subject will receive the same treatment as the subject being replaced.

8.3.5.5 Stopping Rules for Part A and Part B

In the assessment whether AE related criteria for halting or stopping are met, special attention will be paid to any AE that is classed by the investigator as:

- A sign or symptom of bacterial, fungal or viral infection.
- An intestinal disorder.
- A hematological abnormality.

Dosing within a dose cohort will be stopped and further dosing will be halted until unblinded safety information (of the subject with the event) can be reviewed in case of one or more of the following occurring at any time during the observation period in the ongoing cohort:

1. A clinically significant AE that in the opinion of the Investigator, BMS Study Director and PRA Medical Monitor, indicates that the limits of safety and tolerability have been met, and precludes further safe dosing of subjects.
2. Two or more subjects with a severe or serious AE considered to be related to the study drug.
3. Two or more subjects with a serious infection event or 1 subject with opportunistic infection requiring systemic therapy (assessed as related to study drug).
4. Two or more subjects with liver function test elevations (confirmed by repeat) in the absence of an alternative explanation, including:
 - aspartate aminotransferase (AST) or alanine aminotransferase (ALT) > 5 x upper limit of normal (ULN)
 - AST or ALT > 3 x ULN with symptoms consistent with hepatic inflammation
5. One or more subjects with liver function test elevations (confirmed by repeat) consistent with drug-induced liver injury, in the absence of an alternative explanation, including:
 - AST or ALT > 3 x ULN and total bilirubin > 2 x ULN
6. Two or more subjects have a greater than 60 msec increase in QTcF from the baseline value or a QTcF of > 500 msec (confirmed by repeat ECG).

Pending review of all pertinent information collected to date, one of the following decisions may be made:

- To continue dosing the remaining subjects of the cohort as planned, or
- To reduce the dose and continue dosing the remaining subjects of the cohort at the modified dose level (or placebo), or
- To terminate further dosing in the ongoing cohort.

In case of one or more occurrences as listed above, **dose escalation** will be halted until unblinded safety information for the subject(s) in the last completed cohort and with the event(s) can be reviewed. Pending review of all pertinent information collected to date, one of the following decisions may be made:

- To escalate to the next dose level as planned, or
- To escalate to a lower dose level than planned, or
- To extend the last cohort with more subjects exposed to the same dose level (or placebo), or
- To de-escalate, and to dose the next cohort to a lower dose than evaluated in the last cohort (or placebo), or
- To terminate further dose escalations in the relevant study part; subsequent study parts may be continued with amended dose level(s).

In addition, the Sponsor and Investigator may decide to halt dosing within a panel or dose-escalation for reasons not defined above, including but not limited to observing trends in a given dose panel and/or across dose panels.

If any of the above criteria are met within a dose level, dosing will be put on hold and all safety data available across the study will be evaluated to estimate the risk of continuing dosing at the current level and/or proceeding to the higher dose level. The review may include unblinding of the subject(s) that experienced AEs listed above. In addition, the unblinded data set may include subjects from a dose panel, or if appropriate, all treated subjects to date. Unblinding recommendation must be approved by the Sponsor's safety physician.

The maximum acceptable dose will be the dose level below the dose level at which the stopping criteria are met, unless it is determined that a lower dose should be designated as the maximum acceptable dose.

8.4 Treatment

Study treatment is defined as any investigational treatment(s), marketed product(s), placebo, or medical device intended to be administered to a study subject according to the study randomization or treatment allocation.

Study treatment may include both IP and non-IP and is described in [Table 9](#). In this protocol only administration of IP is planned.

An IP, also known as Investigational Medicinal Product (IMP) in some regions, is defined as a pharmaceutical form of an active substance or placebo being tested or used as a reference in a clinical study, including products already with a marketing authorization but used or assembled (formulated or packaged) differently than the authorized form, or used for an unauthorized indication, or when used to gain further information about the authorized form.

Other medications used as support or escape medication for preventative, diagnostic, or therapeutic reasons, as components of the standard of care for a given diagnosis, will be considered as non-IPs.

Table 9 Study Treatments for IM024 005

Product Description / Class and Dosage Form	Study Part/Cohort	Potency	IP/Non-IP	Blinded or Open Label	Packaging / Appearance	Storage Conditions (per label)
BMS-986251 / oral solution	Part A and Part B	1 mg/mL and 20 mg/mL	IP	Blinded	On-site compounded solution [#]	Refer to the label on container and/or pharmacy manual
Placebo for BMS-986251 / oral solution	Part A and Part B	N/A	IP	Blinded	On-site compounded solution [#]	Refer to the label on container and/or pharmacy manual
BMS-986251 / oral suspension (under development)	Part A – BA/FE cohort only	Depending on final formulation	IP	Open label	Depending on formulation*	Refer to the label on container and/or pharmacy manual
BMS-986251 / tablet (under development)	Part C	Depending on final formulation	IP	Blinded	Formulated tablet in a bottle	Refer to label on container and/or pharmacy manual
Placebo for BMS-986251 / tablet (under development)	Part C	N/A	IP	Blinded	Formulated tablet in a bottle	Refer to label on container and/or pharmacy manual

IP = investigational product; N/A = not applicable.

[#] The composition of the oral solution vehicle and placebo is 50/15/35 %w/w PEG-400 (polyethylene glycol-400)/TPGS (Tocopherol Polyethylene Glycol Succinate)/200mM Tris (trisaminomethane) buffer pH 9.

* The suspension formulation is under development. All excipients will be of compendial grade.

8.4.1 Treatments Administered

The Investigator must ensure that the IP will be used only in accordance with the protocol.

8.4.1.1 Part A – SAD in Healthy Volunteers

In the morning of Day 1, after fasting for at least 10 hours, each subject will receive a single oral dose of BMS-986251 or placebo at approximately 9:00 AM as an oral solution of up to a planned volume of 6 mL, depending on the dose level. The medication time is provided as an indication only (for scheduling purposes).

Subjects enrolled in the BA/FE cohort will receive a second single oral dose of BMS-986251 at approximately 9:00 AM on the morning of Day 1 of Period 2, as an oral suspension (under development; representative for the solid dosage form to be used in Part C), after a 10-hour overnight fast. These subjects will receive a third single oral dose of BMS-986251 at approximately 9:00 AM on the morning of Day 1 of Period 3, as an oral suspension, 30 minutes after start of consumption of a high-fat breakfast. The high-fat breakfast (see [Appendix 5](#)) has to be consumed completely in 20 minutes. The exact time of start and end of breakfast and the exact time of dosing will be recorded in the eCRF. Washout between single dose administrations will be at least 2 weeks, based on an anticipated terminal half-life of BMS-986251 of approximately 40 hours.

In all study periods, at the time of dosing, a total of 240 mL of water will be administered to the subjects in all cohorts along with his/her dose of study drug. The time of BMS-986251/placebo administration will be called “0” hour. The exact time of dosing will be recorded in the eCRF. Subjects will remain fasted until at least 4 hours after administration. Water is allowed during fasting, except for 2 hours before and 1 hour after administration.

8.4.1.2 Part B – MAD in Healthy Volunteers

In the morning of Days 1-14, each subject will receive a single oral dose of BMS-986251 or placebo at approximately 9:00 AM as an oral solution of up to a planned volume of 6 mL, depending on the dose level. The medication time is provided as an indication only (for scheduling purposes). On Days 1 and 14, subjects will fast for at least 10 hours prior to dosing. At the time of dosing, 240 mL of water will be administered to the subject along with his/her dose of study drug. The time of first dose administration will be called “0” hour; all other time points will be relative to time “0”. The exact time of dosing will be recorded in the eCRF. On Days 1 and 14, subjects will remain fasted until at least 4 hours after administration. Water is allowed during fasting, except for 2 hours before and 1 hour after administration.

On Days 2 to 13, BMS-986251 or placebo will be administered in the fasted state. After dosing, subjects will continue their fast until breakfast. The breakfast will be provided approximately 2 hours after dosing. Water is allowed during fasting, except for 2 hours before and 1 hour after administration.

8.4.1.3 Part C – Multiple Dosing in Psoriasis Patients

Sub-cohort with intensive PK sampling

On Days 1 and 14, subjects will be dosed in the CRU following an overnight stay. They will receive a single oral tablet dose of BMS-986251 or placebo at approximately 9:00 AM in the morning, after an overnight fast of at least 10 hours prior to dosing. The medication time is provided as an indication only (for scheduling purposes). At the time of dosing, 240 mL of water will be administered to the subject along with his/her dose of study drug. The time of first dose administration will be called “0” hour; all other time points will be relative to time “0”. The exact time of dosing will be recorded in the eCRF. On Days 1 and 14, subjects will remain fasted until at least 4 hours after administration. Water is allowed during fasting, except for 2 hours before and 1 hour after administration.

On Day 2 subjects will be dosed in the CRU, after an overnight fast. Breakfast will be given after dosing. The minimum time between dosing and breakfast will be determined based on the results of the FE investigation in Part A. Prior to discharge, subjects will be given a dosing diary and study drug will be dispensed for at-home administration in the mornings on Days 3-6 and 8-13. Study treatment will be supplied as tablets in a bottle. Subjects will be instructed to take study drug at approximately the same time every morning on an empty stomach and are instructed to record the time of their taken dose in their dosing diary. Results from the FE investigation in Part A may lead to different dosing instructions. If a subject forgets a dose, but remembers within approximately 12 hours of the expected dose, the dose should be taken. If it is past 12 hours, that dose should be missed and the next expected dose should be taken at the usual time.

On Day 7, subjects will not take their morning dose at home, but instead bring their study drug and dosing diaries to the CRU for administration of the dose after completion of pre-dose procedures.

Sub-cohort with sparse PK sampling

Patients enrolled in the sub-cohort with sparse PK sampling will receive the first dose of study drug in the CRU. The study drug will be taken with 240 mL of water. In addition, on Days 7 and 14 the patients will also receive their doses in the CRU. The remaining doses between Days 2-6 and 8-13 will be taken at home. On Day 1, subjects will be given a dosing diary and study drug will be dispensed for at-home administration in the mornings on Days 3-12. Study treatment will be supplied as tablets in a bottle. Subjects will receive the same dosing instructions for dosing at home as above.

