Physician Global Assessment (PGA) score			X												X		X
Dermatology Life Quality Index (DLQI)			X												X		X
Adverse events	X			X													
Serious adverse events				X													

BMI = body mass index; CYP = cytochrome P450; DLQI = Dermatology Life Quality Index; ECG = electrocardiogram; FSH = follicle stimulating hormone; HBsAg = hepatitis B surface antigen; HCV = hepatitis C virus; HIV = human immunodeficiency virus; hrs = hours; IL-17 = interleukin-17; IL-22 = interleukin-22; NK = natural killer; PASI = Psoriasis Area and Severity Index; PGA = Physician Global Assessment; PK = pharmacokinetic; TBNK = T, B, and NK cells

Table 4 Study Procedural Outline Part C – MAD Psoriasis Patients – Sparse PK Sampling Sub-Cohort (IM024 005)

Visit	Screening	Pre-Treatment	Treatment			Follow-up
			1	7	14	
Study Days	-21 to -1	1	1	7	14	28
Ambulant visit	X	X	X	X	X	X
Informed consent and medical history	X					
Demographics	X					
Physical examination	X					X
Genotyping (CYPs, transporters)		X				
Vital signs	X	X		X	X	X
Body weight and height (including BMI calculation) ¹	X	X				X
Eligibility check	X	X				
12-lead ECG	X	X			X	X
Clinical laboratory, hematology incl. reticulocytes	X	X			X	X
Drug and alcohol screen	X	X			X	X
HBsAg, anti-HCV, and anti-HIV 1/2 tests	X					
Quantiferon Gold test	X					
FSH (females only)	X					
Pregnancy test (females only)	X	X				X
Randomization		X				
Study drug administration ²			X			
Previous and concomitant medications	X		X			
PK sampling blood ³		X		X	X	
Sampling for ex-vivo IL-17 inhibition in whole blood		X		X	X	X
Sampling for IL-17, IL-22, β -defensin, and erythropoietin		X		X	X	X
Sampling for T, B, and NK cell (TBNK), $\gamma\delta$ T cells, T cell subsets.		X		X	X	X
Plaque biopsy for immunochemistry and RNA analysis		X			X	
Psoriasis affected body area	X	X				
Psoriasis Area and Severity Index (PASI) score		X		X	X	X

¹ Height will only be measured at screening. BMI will also only be calculated at screening.² Study drug will be administered in the clinical research unit on Days 1, 7, and 14. On Days 2-6 and 8-13, subjects will take the study drug at home.³ Pre-dose PK blood sampling on Days 1, 7 and 14

Visit	Screening	Pre-Treatment	Treatment			Follow-up
Study Days	-21 to -1	1	1	7	14	28
Physician Global Assessment (PGA) score		X		X	X	X
Dermatology Life Quality Index (DLQI)		X		X	X	X
Adverse events			X			
Serious adverse events	X					

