8.1.3 Part C, Multiple Dose in Psoriasis Patients

Part C will be initiated after thorough review of safety, tolerability, PK and PD data (as available) from Part A and Part B, and after verification that administration of BMS-986251 is safe and tolerable enough to administer in psoriasis patients.

In Part C, a total of 15 patients with moderate-to-severe psoriasis will be enrolled in 2 sub-cohorts: 1 sub-cohort with intensive PK sampling and 1 sub-cohort with sparse PK sampling.

At least 6 patients will be enrolled in the sub-cohort with intensive PK sampling. The patients enrolled in this cohort will be admitted to the CRU on the day prior to first drug administration (Day -1). Patients will be dosed with the first dose of BMS-986251 on Day 1 and will be discharged on Day 2 after intake of the 2nd dose. Between Day 3 and Day 12, the patients will take the medication once daily (QD) at home, except on Day 7. Treatment compliance information will be collected while subject is dosing at-home via dosing diaries. Patients will return to the CRU for an ambulatory visit on Day 7 and will be instructed not to take their morning dose at home, but instead bring their study drug and dosing diaries to the CRU for administration following pre-dose procedures. Should compliance be lower than expected, subjects will be counselled on dose administration. Patients will be re-admitted to the CRU for a second stay on Day 13. Subjects will receive their final dose on Day 14. They will be discharged on Day 15 (24 hours after intake of the last dose). Follow-up assessments will be on Day 28.

Patients who are not available for 2 in-clinic periods will be enrolled in the sub-cohort with sparse PK sampling. These patients will visit the CRU for ambulatory assessments on Day 1 in the morning (first dose) and on Days 7, 14, and 28, with follow-up assessments on Day 28. On Day 1 they will receive the first dose in the CRU. In addition, on Days 7 and 14 the patients will also receive their doses in the CRU. The remaining doses between Days 2-6 and

8-13 will be taken at home. Treatment compliance information will be collected while subject is dosing at-home via dosing diaries.

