9.3 Endpoints

9.3.1 Primary Endpoints

The primary objective to assess the safety, tolerability and PK of single and multiple oral doses of BMS-986251 in healthy subjects and in patients with moderate-to-severe psoriasis will be measured by the following primary endpoints:

Safety and tolerability

- Number and percent of subjects that experience the following: SAE, death or an AE leading to study discontinuation, during the study participation or up to 1 month post discontinuation of dosing or last participation in the study for SAE.
- Number and percent of subjects with potentially clinically significant changes in ECG parameters, vital signs, or clinical laboratory parameters from Day 1 through the final follow visit.

Other safety measures collected during the study are not considered among the primary endpoint and will be summarized as safety endpoints. Stopping rules for safety are discussed in Section 8.3.5.5.

Pharmacokinetics

PK parameters will be derived from BMS-986251 concentration versus time data measured at the time points specified in the schedule of assessments for each part of the study. The PK parameters to be assessed are listed in Section 8.5.3. The PK parameters to be evaluated in each part include but are not limited to the following:

- Part A: C_{max} , t_{max} , AUC_{0-t} , AUC_{0-inf} , $t_{1/2}$, CL/F , V_z/F , Ae_t , $Fe_{urine}\%$, CL_R
- Part B:
Day 1: C_{max} , t_{max} , AUC_{0-t} , AUC_{0-24}
Days 2-14: C_{pre}
Day 14: C_{max} , t_{max} , AUC_{0-t} , AUC_{0-24} , CL/F , V_z/F , $t_{1/2}$, $AR_{AUC0-24}$, $AR_{C_{max}}$, Ae_t , $Fe_{urine}\%$, CL_R
- Part C (intensive PK sampling sub-cohort):
Day 1: C_{max} , t_{max} , AUC_{0-t} , AUC_{0-24}

- Days 2-14: C_{pre}
- Day 14: C_{max} , t_{max} , AUC_{0-t} , AUC_{0-24} , CL/F , V_z/F , $t_{1/2}$, $AR_{AUC_{0-24}}$, $AR_{C_{max}}$
- Part C (sparse PK sampling sub-cohort):
Days 7 and 14: C_{pre}

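### Protocol 8.4.1.3 dispenses home doses to the sparse-PK psoriasis patients for Days 3-12, but their home-dosing days are 2-6 and 8-13

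*Protocol*

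**What the plan says.** **Sparse PK sub-cohort.** Protocol 8.4.1.3 gives the first dose in the clinical research unit (CRU) on Day 1 and then states: "In addition, on Days 7 and 14 the patients will also receive their doses in the CRU". It continues: "The remaining doses between Days 2-6 and 8-13 will be taken at home". The next sentence hands over the diary and the drug on Day 1 and says that "study drug will be dispensed for at-home administration in the mornings on Days 3-12". The form of supply is given without a count: "Study treatment will be supplied as tablets in a bottle".

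Table 4 footnote 2 in the Schedule of Activities agrees with the first version of the days: "On Days 2-6 and 8-13, subjects will take the study drug at home". Section 8.1.3 also gives Days 2-6 and 8-13 for this sub-cohort. Table 8 sets the regimen at 60 mg once daily for 14 days.

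**Intensive PK sub-cohort.** Section 8.1.3 says: "Between Day 3 and Day 12, the patients will take the medication once daily (QD) at home, except on Day 7". Section 8.4.1.3 and Table 3 footnote 6 instead give Days 3-6 and 8-13 as the home days, so they include Day 13.

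**Endpoint.** For the sparse sub-cohort, Section 9.3.1 lists one PK parameter among the primary endpoints: the pre-dose concentration on Days 7 and 14.

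**The concern.** Two consecutive sentences of 8.4.1.3 give different home-dosing days for the same patients. The second of them is the one that tells a site which days to dispense for, so it is an instruction and not background text.

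The sparse patients attend only on Days 1, 7, 14 and 28. Unlike the intensive patients, they have no CRU contact on Day 2 or Day 13. A home dose missing from the supply would therefore not be given at a scheduled visit instead. Day 13 is the sensitive day, because its dose is the last one before the Day 14 trough, and that trough is one of only two PK endpoint values per patient in this sub-cohort.

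**Working it through.** **1. Which set of days fits the regimen?**

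| Set | Days | Count |
|---|---|---|
| CRU doses | 1, 7, 14 | 3 |
| Home doses (8.4.1.3 preceding sentence, 8.1.3, Table 4 footnote 2) | 2-6, 8-13 | 5 + 6 = 11 |
| Dispensing sentence | 3-12 | 10 |

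- CRU plus home days: 3 + 11 = 14 doses, with no gap and no overlap. This reproduces the 14-day once-daily regimen of Table 8.
- Home days that the dispensing sentence covers: 3-6 and 8-12, which is 4 + 5 = 9 of 11.
- Home days that it omits: 2 and 13. CRU day that it includes: 7.
- CRU days plus Days 3-12: 12 distinct dosing days out of 14, with Day 7 counted in both sets.

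Only Days 2-6 and 8-13 complete the regimen, so the dispensing sentence is the one in error.

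**2. Where would a shortage fall?**

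The bottle is handed over on Day 1. Suppose that a site read the sentence as a quantity of 10 daily doses.

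- If the Day 7 CRU dose does not come from the bottle, Days 2-6 and 8-12 use 5 + 5 = 10 doses, and Day 13 is short.
- If the Day 7 dose also comes from the bottle, Days 2-11 use 10 doses, and Days 12 and 13 are short.

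**3. What would that do to the Day 14 trough?**

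Inputs: a 24 h dosing interval and an anticipated terminal half-life of about 40 h (Protocol 8.1.1). Assumptions: linear kinetics, mono-exponential decline with absorption time ignored, equal doses, and every other dose taken. No patient half-life is given, so 30 h and 50 h are shown as an assumed range.

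- Fraction remaining after one interval: r = 2^(−24/40) = 0.6598.
- Full Day 14 trough, in units of one dose's initial concentration: Σ r^i for i = 1 to 13 = 1.9303.
- Loss if Day 13 is missed: r / 1.9303 = 0.6598 / 1.9303 = 0.342.
- Loss if Days 12 and 13 are missed: (r + r²) / 1.9303 = (0.6598 + 0.4353) / 1.9303 = 0.567.

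| Half-life | r | Σ r^i, i = 1 to 13 | Day 13 missed | Days 12 and 13 missed |
|---|---|---|---|---|
| 30 h (assumed) | 0.5743 | 1.3483 | 42.6% lower | 67.1% lower |
| 40 h (protocol) | 0.6598 | 1.9303 | 34.2% lower | 56.7% lower |
| 50 h (assumed) | 0.7170 | 2.4998 | 28.7% lower | 49.3% lower |

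**4. How many patients?** At least 6 of the 15 go to the intensive sub-cohort (8.1.3), so at most 15 − 6 = 9 would be affected.

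**5. Intensive sub-cohort.** Section 8.1.3 gives Days 3-12 without Day 7, which is 9 home doses. Section 8.4.1.3 and Table 3 footnote 6 give 4 + 6 = 10. The difference is Day 13, the day of re-admission, and 8.1.3 does not say where that dose is taken.

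**The case against.** The strongest case on the other side is that this is a slip that no careful reader would act on. The right days are stated three times, once in the sentence immediately before. A once-daily regimen for 14 days cannot be squared with two undosed days. The Day 7 visit gives the site a chance to top up the bottle, and the dosing diaries would show a missed dose when the trough is interpreted. No tablet count is visible and the Part C compliance text is not shown, so no shortage is demonstrated. The Part C text was also provisional: the tablet was still under development, and fasted or fed dosing was undecided. All of this stands. It limits the consequence, but it does not make the sentence correct.

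A reader might infer more, namely that patients would have no drug for the Day 2 dose and that the Day 7 trough would therefore be low as well. The documents do not support that. The bottle is in the patient's hands from Day 1, so missing Day 2 would mean withholding an available dose against the preceding sentence. A short supply runs out at the end, not at the start. No effect on the Day 7 trough follows.

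Nor was Days 3-12 a deliberate design feature. Nothing in the protocol presents it as one, and the design itself is clear from the other three statements.

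On the intensive sub-cohort, the objection has some force against relying on Table 3 alone. The table marks a Day 13 administration in the column that it shares with Day -1, and footnote 6 places that dose at home. That is a reason to say in 8.1.3 where the dose is taken.

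**Conclusion.** The inconsistency is real and is confined to wording. The sparse dispensing sentence in 8.4.1.3 covers 9 of 11 home doses and names one clinic-dosed day. The severity is minor: this is a drafting error in an operative instruction.

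The possible effect is a Day 14 trough about 34% lower in a patient who misses only Day 13 (29% to 43% over assumed half-lives of 50 h to 30 h), or about 57% lower if Days 12 and 13 are both missed. These figures rest on linear kinetics, on the anticipated half-life, and on a site actually dispensing a 10-day supply that is not corrected at Day 7. None of the documents shows that last condition being met.

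SAP 7.1 confirms that Part C was not conducted, so no patient or data were affected. No sample size or planned test depends on the sentence. The correction matters only if the Part C text is reused.

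**What to change.** - In the sparse dispensing sentence of Protocol 8.4.1.3, replace Days 3-12 with Days 2-6 and 8-13.
- In Protocol 8.1.3, change the intensive sub-cohort's home window to Days 3-6 and 8-13, matching 8.4.1.3 and Table 3 footnote 6. State that the Day 13 dose is taken at home in the morning, before re-admission. That also settles how the Day 13 entry in Table 3 is to be read.

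The cost is one phrase and one sentence of protocol wording. Visits, sampling, sample size and analysis do not change.
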